9.6 DATA MANAGEMENT

Data collection is the responsibility of the clinical trial staff at the site under the supervision of the principal investigator. During the study, the investigator must maintain complete and accurate documentation for the study.

Designated CRO will serve as the statistical and data coordinating center for this study and will be responsible for data management, quality review, analysis, and reporting of the study data.

The data from enrolling patients in this study will be recorded on a CRF or other applicable forms. The designated CRO will capture, check, store, and analyze the data. The designated CRO will follow Boehringer Ingelheim standard operating procedures (SOPs) and their own internal SOPs.

A data management plan (DMP) will be created to describe all functions, processes, and specifications for data collection, cleaning, and validation. Validation process will be performed as outlined in a data validation plan (DVP). Queries will be reviewed and sent to the study investigators for clarification. Designated site staffs for investigation are required to reply the queries and make any necessary changes to the data. The queries will be resolved and data will be updates under the agreement of investigator. Once all queries have been resolved, the database will be locked. The locked data will be exported to generate the subject listings, tabulations, and statistical analyses.

Data will be transferred to Boehringer Ingelheim after the closure of the study.

NIS Protocol Page 32 of 46

9.7 DATA ANALYSIS

Analyses will be performed by a designated CRO. The main analysis population will consist of all eligible patients (i.e., all patients who have signed the informed consent and fulfilled all inclusion criteria and no exclusion criteria).

Analytic specifications, including tables and listings, will be detailed in the statistical analysis plan (SAP) that is separate from the full study protocol. A change to the data analysis methods described in the study protocol will require an amendment only if it changes a principal feature of the study objective. Additional exploratory analyses of the data will be conducted as deemed appropriate.

All statistical assessments will be performed using Statistical Analysis Software (SAS®) Version 9.4 or higher (SAS Institute, Cary, NC, USA).

9.7.1 Main analysis

The analyses will be mainly descriptive to gain an understanding of the characteristics of the sample studied.

Continuous variables will be reported as number, mean, standard deviation (SD), minimum, maximum, and 95% confidence interval (CI). Categorical variables will be summarized as number and frequency or percentage with observed (non-missing) data.

Analysis of endpoints:

- The primary outcome is to describe the proportion of patients with high adherence to dabigatran treatment which is defined as achieving MMAS-8 score of 8 points at 12 months for each group. Subjects without MMAS-8 value recorded at 12 months will be excluded from the analysis of primary endpoint.
- The Mean MMAS scores at 3, 6, 9 and 12 months will be compared between patients with and without advanced educational intervention using Chi-square, Fisher's exact, or other appropriate tests for categorical data and using t-test or Wilcoxon rank-sum test for continuous data. Similarly, subjects without MMAS-8 value recorded at a specific visit will be excluded from the analysis of corresponding secondary endpoints.
- Other secondary outcomes in patients with and without advanced educational intervention separately and further outcomes only within pooled patient set (e.g., comorbidities, stroke/thromboembolic/bleeding events, risk factors, ADR, etc.) will all be analyzed in a descriptive manner
- All tests will be done under a statistical level of 0.05.

NIS Protocol Page 33 of 46

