Non-Interventional Study (NIS) Protocol

Document Number:	c32188789-01	
BI Study Number:	1160-0304	
BI Investigational Product(s):	Dabigatran (Pradaxa®)	
Title:	Relationship of Advanced Holding Education and ADherence on antithrombotic in younger NVAF patients	
Brief lay title:	ReAHEAD	
Protocol version identifier:	Version 1.0	
Date of last version of protocol:	NA	
PASS:	No	
EU PAS register number:	Study not registered.	
Active substance:	Dabigatran etexilate mesylate (ATC code: B01AE07)	
Medicinal product:	Dabigatran	
Product reference:	TFDA number: 026233 (75 mg), 025459 (110 mg), 025458 (150 mg)	
Procedure number:	EMA agency product number: EMEA/H/C/000829	
Marketing authorisation	This study is initiated, managed, and financed by:	
holder(s):		
Joint PASS:	No	
Research question and objectives:	The primary objective of this study is to explore whether the advanced educational intervention would improve the adherence to dabigatran, in a 12-month follow-up period for newly diagnosed atrial fibrillation (AF) adult patients under 75 years old.	
	The secondary objectives are to describe comorbidities and VASc score at baseline and at the end of the study; and to describe stroke, thromboembolic events, and bleeding events in dabigatran	

NIS Protocol Page 2 of 46

	patients (with or without advanced educational intervention) in a 12-month follow-up period for AF adult patients under 75 years old.
Country(-ies) of study:	Taiwan
Author:	
	Title:
	Name:
	Tel:
	Mobile:
	Fax:
	Email:
Marketing authorisation	
holder(s):	Title:
	Name:
	Tel:
	Mobile:
	Fax:
	Address:
	Email:
In case of PASS, add: MAH contact person:	Not applicable
In case of PASS, add: <eu-qppv:></eu-qppv:>	Not applicable
In case of PASS, add: <signature eu-="" of="" qppv:=""></signature>	Not applicable
Date:	21-Oct-2020
	Page 1 of 46
	Proprietary confidential information Boehringer Ingelheim Group of companies. All rights reserved. in part - be passed on, reproduced, published or otherwise used without prior written permission

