7. RATIONALE AND BACKGROUND

Atrial fibrillation (AF) is the most common sustained cardiac arrhythmia, and it is a global problem. The overall prevalence of atrial fibrillation (AF) in Taiwanese was 1.4% in men and 0.7% in women in 2008 and is estimated to be 4.01% in 2050. Patients with AF face a strongly elevated risk of stroke—about 3- to 5-fold higher after adjustment for risk factors. According to an analysis of AF patients without treating any antiplatelet or oral anticoagulant (OAC) from the National Health Insurance Research Database (NHIRD; 1996 – 2011) of the whole Taiwanese population, the event rate of ischemic stroke in AF patients with VASc score from 0 to 7 points was increasing from 1.1 to 13.33 per 100 person-years.

Treatment adherence

Lifelong OAC therapy is the preferred treatment for the prevention of thromboembolic events in the majority of patients with AF. Adherence to medication is essential for valid treatment for OAC therapy. Non-adherent patients (proportion of days covered for new oral anticoagulants [NOAC] is < 80%) were reported to be 2.08 times more likely to experience the ischemic stroke compared to the adherent patients in one year. A retrospective study from the USA of evaluating the adherence rate of OACs by Morisky 8-Item Medication Adherence Questionnaire (MMAS-8) score found a high adherence (MMAS-8 score reaches 8) rate of 71% to dabigatran and concluded that the adherence could be attributed to differences in health knowledge and duration taking anticoagulant medication.

Age is another influencing factor of adherence. Younger patients have significantly worse adherence compared to older ones⁹ because of their low awareness of risks of AF and benefits of AF treatments regarding the prevention of ischemic events. Patients under 75 years old might have lower risk scores but their poor adherence may increase the incidence of stroke and the lifetime economic burden (e.g., work loss and premature death). Providing advanced education to patients who are under 75 years old to increase their awareness of the importance of early intervention and drug adherence may be a feasible strategy to enhance the adherence rate to OACs among younger patients, to reduce stroke/or recurrent risk, and to contribute to socioeconomic saving. However, such health education has not been implemented in Taiwan currently.

BOEHRINGER INGELHEIM Group of Companies

NIS Protocol Page 15 of 46

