8. RESEARCH QUESTION AND OBJECTIVES

The primary objective of this study is to explore whether the advanced educational intervention would improve the adherence to dabigatran, in a 12-month follow-up period for newly diagnosed atrial fibrillation (AF) adult patients under 75 years old.

The secondary objectives are to describe comorbidities and VASc score at baseline and at the end of the study; and to describe stroke, thromboembolic events, and bleeding events in dabigatran patients in a 12-month follow-up period for AF adult patients under 75 years old.

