9. RESEARCH METHODS

9.1 STUDY DESIGN

This is a multi-center, 1:1 randomized study to evaluate the effects of educational intervention on adherence to dabigatran, for up to 12 months. The study will be carried out at around 20 hospitals (20 ± 3), where AF patients are mainly treated in Taiwan. A total of 1,200 patients are planned to be enrolled to target 1,000 patients included in the analysis.

Patients newly diagnosed with AF within 1 month, under 75 years old, and newly prescribed with dabigatran on physician's decision per local labelling will be enrolled and equally randomized to receive standard of care (routine clinical practice) or standard of care (routine clinical practice) with advanced educational intervention. To create the randomization numbers, we will use block randomization by Statistical Analysis Software (SAS®) Version 9.4 or higher (SAS Institute, Cary, NC, USA).

The study duration consists of a 1-year enrolment period and a 12-month follow-up period consisting of visits at 3, 6, 9, and 12 months for each individual patient. Being an NIS, the time points of follow-up visits are set in accordance with the routine outpatient follow-ups of AF management in Taiwan. Patients will be continuously followed until death, lost to follow-up, or end of data collection at 12 months, whichever comes first.

The educational materials from "Shared decision making of treatment of NOAC in AF patients" (NTA: 180647) and "Atrial Fibrillation Patient Care in Hospitals" (NTA: 190707) will be used as the educational materials for the experimental group. The education materials will be delivered after randomization (baseline); and at 3, 6, and 9 months thereafter. The adherence to dabigatran will be measured by MMAS-8 score at 3, 6, 9, and 12 months.

The comorbidities, VASc score, and HAS-BLED score will be recorded at baseline; and at 3, 6, 9, and 12 months. Stroke, thromboembolic events, and bleeding-related events will also be captured during 12 months of follow-up.

The whole NIS will be implemented by a Contract Research Organization (CRO) under Local Boehringer Ingelheim's governance.

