#### 10. DATA ANALYSIS

The main and further analysis population will consist of all eligible patients (i.e., all patients who have signed the informed consent and have fulfilled all eligibility criteria).

Continuous variables will be reported as number, mean, standard deviation (SD), minimum, maximum, and 95% confidence interval (CI). Categorical variables will be summarized as number and frequency or percentage with observed (non-missing) data. Missing numbers of both continuous and categorical variables will also be summarized.

As for comparisons of continuous data between baseline and follow-up visit, paired-t test will be performed at the significant level of 0.05. Shapiro—Wilk test will be performed to test the normality of data. When normality assumption is violated, Wilcoxon signed-rank test will be performed instead. On the other hand, McNemar's test will be performed to for comparisons of categorical data between baseline and follow-up visit at the significant level of 0.05.

For the endpoints pre-identified to compare between patients with and without advanced educational intervention, the analyses will be done by independent t-test for continuous data at the significant level of 0.05. Shapiro–Wilk test will be performed to test the normality of data. When normality assumption is violated, Wilcoxon rank-sum test will be performed instead. On the other hand, Chi-square or Fisher's exact test will be performed to for comparisons of categorical data at the significant level of 0.05.

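### The protocol pre-specifies no by-arm summary of stroke, thromboembolic or bleeding events or ADRs in a 1:1 randomised study

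*Protocol*

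**What the plan says.** Protocol 9.1 describes a "1:1 randomized study to evaluate the effects of educational intervention on adherence to dabigatran" and adds: "Stroke, thromboembolic events, and bleeding-related events will also be captured during 12 months of follow-up". Protocol 11.2 also requires collection of all ADRs and all adverse events with fatal outcome.

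Protocol 9.7.1 treats two groups of outcomes differently within one sentence. Other secondary outcomes are shown separately for patients with and without the intervention, whereas "further outcomes only within pooled patient set (e.g., comorbidities, stroke/thromboembolic/bleeding events, risk factors, ADR, etc.) will all be analyzed in a descriptive manner". The data-analysis part of the abstract (Protocol 4) gives the same rule, again "further outcomes only within pooled patient set".

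The matching objective in Protocol 8 is "to describe stroke, thromboembolic events, and bleeding events in dabigatran patients in a 12-month follow-up period". It states no contrast between arms. The title-page version refers to "patients (with or without advanced educational intervention) in a 12-month follow-up period", which names both arms but promises no comparison. The rationale in Protocol 7 is that education may raise adherence "to reduce stroke/or recurrent risk, and to contribute to socioeconomic saving".

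In the visible SAP text, the between-arm tests cover MMAS-8 adherence, dabigatran discontinuation and its reasons (SAP 10.1), and baseline covariates (SAP 7.1.3). SAP pages 18 and 25, where further outcomes may be described, carry almost no visible text.

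**The concern.** The study exists to change how reliably patients take an anticoagulant. If education works, the natural next questions are whether thromboembolic events fell and whether bleeding rose. Allocation is randomised and the events are recorded in both arms, so by-arm figures are available at little cost. The word *only* in Protocol 9.7.1 rules them out of the planned tables.

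At stake is the completeness of the report. It could present an adherence gain by arm while a reader could not see how many bleeds, strokes, ADRs or deaths occurred in each group. If by-arm figures appear only later, as an unplanned exploratory analysis, the decision to show them may depend on what they look like. The adherence analysis itself is unaffected.

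**Working it through.** **1. The plan's own figures.** The documents give no event rate on dabigatran, no expected event count and no power for clinical events, so there is no stated event figure to reproduce. The only size figure is in Protocol 9.5: 1,200 enrolled, 20% drop-out, 1,000 completing. In fact 1,200 × 0.80 = 960, and 1,000 / 0.80 = 1,250. That mismatch is a separate matter and nothing here depends on it. With 1:1 allocation, 1,200 gives 600 per arm and 1,000 gives 500 per arm. Protocol 9.7.3 keeps data already collected on withdrawals, so 600 is a fair starting denominator.

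**2. What the pooled table hides.** These rates are assumptions chosen for illustration.
- Bleeding in 2% versus 4%: 12 + 24 = 36 of 1,200, pooled 3.0%.
- Bleeding in 3% versus 3%: 18 + 18 = 36 of 1,200, pooled 3.0%.

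The pooled rows are identical. By arm, the first case has a difference of 2.0 points with SE = √[(0.04 × 0.96 + 0.02 × 0.98)/600] = 0.983 points. The 95% CI is 2.0 ± 1.96 × 0.983 = 0.07 to 3.93 points. With 500 per arm the SE is 1.077 points and the interval is about −0.1 to 4.1.

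**3. Precision over a range of assumed 12-month risks.** The half-width of the 95% CI for the risk difference, with the same risk p in both arms, is 1.96 × √[2p(1 − p)/n].

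| Assumed risk | Events per arm (n = 600) | Half-width, n = 600 | Half-width, n = 500 |
|---|---|---|---|
| 1% | 6 | 1.1 points | 1.2 points |
| 2% | 12 | 1.6 points | 1.7 points |
| 3% | 18 | 1.9 points | 2.1 points |
| 5% | 30 | 2.5 points | 2.7 points |

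For orientation, the power of a two-sided 0.05 test at 600 per arm to detect a doubling from 1%, 2% or 5% is 30%, 53% and 91%. For a halving it is 17%, 30% and 63%.

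**4. A plausible stroke effect.** Protocol 7 cites 71% high adherence on dabigatran and a 2.08-fold ischemic stroke risk in non-adherent patients. Assume a 10-point adherence gain and a yearly risk r of 1% to 5% in adherent patients.
- Control risk: r × (0.71 + 0.29 × 2.08) = 1.313r.
- Education risk: r × (0.81 + 0.19 × 2.08) = 1.205r.
- Risk ratio: 1.205/1.313 = 0.92.
- At r = 1%: 1.31% versus 1.21%, a difference of about 0.1 points.
- At r = 5%: 6.57% versus 6.03%, a difference of about 0.5 points.

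These differences are small beside the half-widths in step 3. Power at 600 per arm is about 4% to 6%, and only 5% to 12% with a 20-point gain. The projection is indicative: the 2.08 ratio was defined on proportion of days covered below 80%, not on MMAS-8.

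**The case against.** The strongest defence is that pooling is what the objective asks for. Protocol 8 sets out to describe events in dabigatran patients, the primary question is adherence, and the rationale explains why education may be worthwhile without making stroke an arm-level endpoint. This stands. A reader might infer that the analysis contradicts the objective, but the documents do not support that. By-arm description is equally compatible with a descriptive objective, so the point is a reporting recommendation.

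A reader might also infer that the SAP pools, citing its sentence "The main and further analysis population will consist of all eligible patients". That sentence says who is analysed, not how results are split, and it equally covers the main analysis, which is by arm. The visible SAP goes beyond the protocol elsewhere: it summarises mean daily dose by study group and tests discontinuation between arms. Its planned tables are in separate mock-up documents. By-arm event tables in the SAP therefore cannot be excluded.

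Nor can one say that the trial is unable to show by-arm events. They could be tabulated from the recorded data, and Protocol 9.7 allows additional exploratory analyses. That clause does not name events by arm, however, and leaves the choice until after the data are seen.

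Low event numbers also stand as an objection to testing. They are not an objection to showing counts by arm.

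Finally, a by-arm contrast should not be called simply unbiased. No masking or event adjudication is described, an educator repeatedly meets one arm only, and the investigator judges event severity and ADR causality. Randomisation protects against baseline confounding, not against differences in ascertainment. ADRs and minor bleeding are the most exposed.

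**Conclusion.** The point holds in limited form. Protocol 9.7.1 and the abstract restrict stroke/thromboembolic events, bleeding and ADRs to the pooled set, so the protocol pre-specifies no by-arm event or safety summary. It rests on the protocol text alone and is consistent with the descriptive secondary objective.

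The gain from changing it is transparency, not a powered answer. At 600 per arm, the difference would be known to within about 1.1 to 2.5 points for assumed risks of 1% to 5%. A large bleeding difference might be visible at the higher risks. A reader might expect by-arm columns to reveal any harm or benefit, but effects of realistic size on stroke would not be detectable. All event risks and the adherence gain used here are assumptions, because the documents give no on-dabigatran event rates.

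**What to change.** In Protocol 9.7.1 and the abstract, replace "further outcomes only within pooled patient set" with wording to the effect of *pooled and by randomised group* for stroke/thromboembolic events, major bleeding, minor bleeding, ADRs and fatal adverse events. Carry the change into the SAP and its mock-up tables if they also pool.

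Keep the pooled column. For each arm, give the number and percentage of patients with at least one event, and add the risk difference with its 95% CI. Label these figures descriptive, with no hypothesis test. State in the report that no masking or adjudication was used, if that is so, and that ascertainment of ADRs and minor bleeding may therefore differ by arm.

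Rates per 100 person-years are optional. If they are used, the SAP must first state rules for time at risk, recurrent events and follow-up after dabigatran is stopped, none of which appears in the visible text.

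The cost is extra columns in tables built from data already collected. Protocol 9.7 requires an amendment for an analysis change only if a principal feature of the study objective changes, which this does not. The downside is wide intervals that readers may over-interpret, so the descriptive label needs to be prominent.

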9.5 STUDY SIZE

Approximately 1,200 patients from around 20 hospitals (20 ± 3) will be enrolled in this study. Assuming a drop-out rate of 20%, it is expected to have 1,000 patients completing the study. The sample size is determined based on the feasibility, planned enrolment period, number of potential patients at selected sites, and expected precision of the estimates. As the selected sites are the hospitals with most AF patients treated with dabigatran in Taiwan from northern to southern areas, the patients recruited into this study will be the representative of the AF population treated with dabigatran and the healthcare settings in Taiwan.

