## 5. RESEARCH QUESTION AND OBJECTIVE

The primary objective of this study is to explore whether the advanced educational intervention would improve the adherence to dabigatran, in a 12-month follow-up period for newly diagnosed atrial fibrillation (AF) adult patients under 75 years old.

The secondary objectives are to describe comorbidities and baseline and at the end of the study; and to describe stroke, thromboembolic events, and bleeding events in dabigatran patients in a 12-month follow-up period for AF adult patients under 75 years old.

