#### 6. RESEARCH METHODS

#### 6.1 STUDY DESIGN

This is a multi-center, 1:1 randomized study to evaluate the effects of educational intervention on adherence to dabigatran, for up to 12 months. The study will be carried out at around 20 hospitals ( $20 \pm 3$ ), where AF patients are mainly treated in Taiwan. A total of 1,200 patients are planned to be enrolled to target 1,000 patients included in the analysis.

Patients newly diagnosed with AF within 1 month, under 75 years old, and newly prescribed with dabigatran on physician's decision per local labelling will be enrolled and equally randomized to receive standard of care (routine clinical practice) or standard of care (routine clinical practice) with advanced educational intervention. To create the randomization numbers, we will use block randomization by Statistical Analysis Software (SAS®) Version 9.4 or higher (SAS Institute, Cary, NC, USA).

The study duration consists of a 1-year enrolment period and a 12-month follow-up period consisting of visits at 3, 6, 9, and 12 months for each individual patient. Being an NIS, the time points of follow-up visits are set in accordance with the routine outpatient follow-ups of AF management in Taiwan. Patients will be continuously followed until death, lost to follow-up, or end of data collection at 12 months, whichever comes first.

The educational materials from "Shared decision making of treatment of NOAC in AF patients" (NTA: 180647) and "Atrial Fibrillation Patient Care in Hospitals" (NTA: 190707) will be used as the educational materials for the experimental group. The education materials will be delivered after randomization (baseline); and at 3, 6, and 9 months thereafter. The adherence to dabigatran will be measured by MMAS-8 score at 3, 6, 9, and 12 months.

The comorbidities, VASc score, and HAS-BLED score will be recorded at baseline; and at 3, 6, 9, and 12 months. Stroke, thromboembolic events, and bleeding-related events will also be captured during 12 months of follow-up.

The whole NIS will be implemented by a Contract Research Organization (CRO) under Local Boehringer Ingelheim's governance.

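### For 12-month stroke, thromboembolic and bleeding events the visible plan provides only counts and percentages in all eligible patients, with no stated denominator rule or allowance for time at risk, although 16.7-20% are expected to leave early

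*Protocol*

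**What the plan says.** **Objective.** SAP section 5 and Protocol section 8 make it a secondary objective "to describe stroke, thromboembolic events, and bleeding events in dabigatran patients in a 12-month follow-up period".

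**Method.** Protocol 9.7.1 places these events among the further outcomes: "further outcomes only within pooled patient set (e.g., comorbidities, stroke/thromboembolic/bleeding events, risk factors, ADR, etc.) will all be analyzed in a descriptive manner". Both documents give one general rule for categorical data; in SAP section 10 it reads "Categorical variables will be summarized as number and frequency or percentage with observed (non-missing) data". Confidence intervals are listed there for continuous variables only. SAP section 10 also sets a single population, all eligible patients, for the main and the further analyses.

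**Follow-up.** SAP 6.1: "Patients will be continuously followed until death, lost to follow-up, or end of data collection at 12 months, whichever comes first". Under Protocol 9.7.3, data collected before withdrawal are kept and no more are sought afterwards. SAP 9.2 rules out imputation.

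**Size.** Protocol 9.5: "Approximately 1,200 patients from around 20 hospitals (20 ± 3) will be enrolled in this study", and "Assuming a drop-out rate of 20%, it is expected to have 1,000 patients completing the study".

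**What cannot be seen.** Protocol numbering skips 9.3.2.3 and 9.7.2, SAP pages 18 and 25 are largely empty, and the mock-up tables are a separate document. Any text specific to the further outcomes probably belongs in these places.

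**The concern.** A patient who leaves at month 4 without an event has no 12-month event status. No visible text says how that patient is counted, and none mentions person-time, a censoring rule or a cumulative incidence estimate. The visible rules point to dividing observed events by all eligible patients. The patient then counts as event-free for eight months that nobody observed, and the percentage falls below the 12-month risk.

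For a descriptive objective the estimate is itself the result. If it is presented as a 12-month incidence, its meaning depends on how many patients left and when. It also differs in kind from the per-100-person-year stroke rates that Protocol section 7 gives as background.

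**Working it through.** **1. The plan's own drop-out figure.**
- 1,200 × (1 − 0.20) = 960, not 1,000.
- 1,000 / (1 − 0.20) = 1,250, not 1,200.
- 1 − 1,000/1,200 = 16.7%.

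The stated 20% and the stated 1,000 completers do not agree, so both 16.7% and 20% are carried forward. The documents do not define drop-out as the end of event follow-up; that is assumed here.

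**2. Model.** The plan gives no expected event rate for this study, so the risks below are assumptions. Let F be the true 12-month risk under a constant hazard λ = −ln(1 − F), and let d be the share who leave, spread evenly over the year with the same hazard as stayers. The mean risk observed in leavers is m = 1 − F/λ. With all 1,200 in the denominator:

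crude = (1 − d) × F + d × m, with SE = √[crude × (1 − crude) / 1,200].

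**3. Example, F = 10%.** λ = 0.10536 and m = 1 − 0.10/0.10536 = 0.0509.
- d = 20%: 0.8 × 0.10 + 0.2 × 0.0509 = 0.0902. SE 0.0083; shortfall 0.0098, or 1.2 SE.
- d = 16.7%: 0.8333 × 0.10 + 0.1667 × 0.0509 = 0.0918. SE 0.0083; shortfall 0.0082, or 1.0 SE.

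**4. Results for other assumed risks.**

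| True 12-month risk | Crude, d = 16.7% | Crude, d = 20% | Shortfall in SE |
|---|---|---|---|
| 1.5% | 1.38% | 1.35% | about 0.4 |
| 5% | 4.6% | 4.5% | 0.7 to 0.8 |
| 10% | 9.2% | 9.0% | 1.0 to 1.2 |

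The relative shortfall is about 8% at d = 16.7% and about 10% at d = 20%.

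**5. Timing of leaving** (d = 20%). The shortfall is about 5% if everyone leaves at month 9, about 15% at month 3, and 20% if all leave straight after baseline.

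**6. Choice of denominator** (F = 10%, d = 20%, equal hazard).
- All eligible patients: 9.0%.
- Completers only, counting only their events: 10.0%, no bias.
- All observed events over 960 completers: 0.0902 / 0.8 = 11.3%, too high.

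**7. Leavers at twice the hazard** (stayers at 10%, d = 20%). The true risk is 0.8 × 0.10 + 0.2 × 0.19 = 11.8%. The crude percentage over all patients is about 10.0% (2.1 SE low). An estimate that censors leavers at last contact gives about 11.0% (0.9 SE low), so it removes a little over half of the error.

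**The case against.** The strongest objection is that the governing text may exist but cannot be seen. The visible protocol wording is only that these outcomes "will all be analyzed in a descriptive manner", and a person-time rate is descriptive too. This stands: the absence of a time-at-risk method is established for the visible text only.

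A reader might infer that the plan scores unobserved months as event-free and that the reported incidence is therefore understated. The documents do not go that far. They state no denominator for these events, and step 6 shows that the direction depends on it. The low figure follows from the all-eligible population in SAP section 10, which is the natural reading but not an explicit instruction.

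A reader might also take the 2-SE shortfall in step 7 as the expected size. It rests on an assumed doubling of hazard in leavers, for which the documents give no support, and the remedy repairs it only in part.

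Patients who die without the event are not part of the problem: with death as a competing event they are correctly non-events at 12 months.

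Finally, the summary is pooled, so no comparison between the education and control groups is distorted, and no visible objective is to compare with the cited background rates. Both points limit the consequence. Neither supplies the missing denominator.

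**Conclusion.** The point holds for the visible text. A secondary objective covering 12 months, in a study that expects 16.7-20% of patients to leave, has no stated denominator and no allowance for time at risk. If all eligible patients are the denominator, leaving is even and risk is equal in leavers, the crude percentage is about 8-10% low in relative terms, roughly 0.4 SE at a true risk of 1.5% and 1.0-1.2 SE at 10%. The event risks are assumptions; the drop-out figures are the plan's. This is a moderate weakness in a descriptive result that is worth correcting, subject to confirmation that the unseen further-outcome text does not already settle it.

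**What to change.** First confirm whether the further-outcome text or the mock-up tables already give a rule. If not, add to SAP section 10, separately for stroke/thromboembolic events, major bleeding and minor bleeding:

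- First events per 100 person-years with exact 95% CI, with time running from the start of follow-up to the first of event, death, last contact or month 12.
- The 12-month cumulative incidence (Aalen-Johansen) with 95% CI, with death as a competing event and withdrawal or loss as censoring.
- Crude counts kept, but the crude percentage not labelled a 12-month incidence.

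Reconcile the 20% drop-out with the 1,000 completers in Protocol 9.5.

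**Cost.** SAP wording and standard SAS output. The visible text has events recorded at each visit and withdrawal reasons on the CRF, but does not list event onset or last-contact dates as fields. Confirm that they are captured, or use visit dates. Intervals will be slightly wider. The estimates rely on non-informative censoring, so bias is reduced but not removed if leavers are at higher risk; the report should say so.
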